### 1 STUDY SUMMARY

	<del>-</del>
Study name	Open prospective study to evaluate the safety, tolerability, pharmacokinetics and the effect of food of medicinal product PBTZ169 in 80 mg capsules when used in increasing doses in
	healthy volunteers
Identification	PBTZ169-Z00-C01-3
number/study code	
Study phase	Phase I
Planned study dates	Expected duration of the study – 7 months.
	Recruitment period is approximately 10 days. Maximum duration
	of participation of one volunteer in the study at the first stage (dose
	escalation when used once or twice, effect of food when used once)
	- 24 days, at the second stage (repeated use) – 30 days.
Study goals	At the first stage – study the safety, tolerability and evaluate the
Study gours	pharmacokinetics of PBTZ169, 80 mg capsules, in healthy
	volunteers when administered once or twice on an empty stomach
	successively in increasing doses (640, 960, 1280 mg once a day and
	640 mg twice daily), evaluate the effect of food with single
	administration of the product at a dose of 640 mg.
	At the second stage – study the safety, tolerability and evaluate the
	pharmacokinetics of PBTZ169, 80 mg capsules, in healthy
	volunteers with repeated use for 14 days, at a dose and following a
	regimen (on an empty stomach or after meal, once a day or twice
	day) determined by results of analysis of tolerability, safety and
	pharmacokinetics after the completion of the first stage of the study.
Study objective	
Study Objective	Main objectives
	• Evaluate the safety and tolerability of PBTZ169, 80 mg
	capsules, in healthy volunteers once or twice on an empty
	stomach in increasing doses (640, 960, 1280 mg once daily
	and 640 mg twice daily) and repeated administration for 14
	days at maximum dose and following a regimen determined
	by results of analysis of tolerability, safety and
	pharmacokinetics after the completion of the first stage of
	the study.
	• Evaluate the effect of food on the pharmacokinetics of
	PBTZ169, 80 mg oral capsules at a dose of 640 mg.
	Compare the test (T) method of administration (8 80 mg
	capsules after meal) with the reference (R) method of
	administration (8 80 mg capsules on an empty stomach).
	Secondary objectives
	• Evaluate the safety of PBTZ169 based on all possible
	adverse events.

- Evaluate the effect of PBTZ169 on vital signs (blood pressure, HR, body temperature, RR) and results of physical examination.
- Evaluate the effect of PBTZ169 on laboratory and instrumental examinations (complete blood count, biochemical blood test, urine analysis, ECG).
- To evaluate the pharmacokinetic parameters of PBTZ169, 80 mg capsules, in healthy volunteers when used once or twice on an empty stomach in increasing doses (640, 960, 1280 mg once a day and 640 mg twice daily): maximum concentration Cmax, time to reach maximum concentration Tmax, area under the pharmacokinetic curve AUC0-t and AUC0-∞, half-life T1/2, total clearance Clt/F, volume of distribution Vd/F, elimination constant kel.
- Evaluate the pharmacokinetic parameters of PBTZ169, 80 mg capsules, with repeated use for 14 days at the maximum dose and following a regimen determined by results of analysis of tolerability, safety and pharmacokinetics after the completion of the first stage of the study in healthy volunteers, namely: maximum concentration of Cmax, residual concentration with repeated use of Ctrough, time to reach the maximum concentration Tmax, area under the pharmacokinetic curve AUC0-t, AUC0-∞ and AUC0-τ, half-life T1/2, total clearance Clt/F, volume of distribution Vd/F, elimination constant kel.

# Planned number of research sites and their location

It is planned to involve up to 2 research sites in the Russian Federation.

#### Design methodology

and

This is an open-label prospective non-comparative study to evaluate the safety, tolerability, pharmacokinetics and the effect of food of medicinal product PBTZ169 in 80 mg capsules when used in increasing doses.

The study will be divided into 2 stages.

### First stage – dose escalation when used once or twice, effect of food with single administration

Volunteers who meet the selection criteria for the study will be included in 5 cohorts:

✓ Cohort 1A (C1A) – includes 10 healthy volunteers of the main group, each of whom will receive PBTZ169 only twice: during period 1 of the *First stage* of the study on an empty stomach at a dose of 640 mg (8 80 mg capsules once a day) and during period 2 of the *First stage* of the study after meal at a dose of 640 mg (8 80 mg capsules, once a day) and 1 healthy backup volunteer.

- ✓ Cohort 1A (C1A) includes 10 healthy volunteers of the main group, each of whom will receive PBTZ169 only twice: during period 1 of the *First stage* of the study after meal at a dose of 640 mg (8 80 mg capsules once a day) and during period 2 of the *First stage* of the study on an empty stomach at a dose of 640 mg (8 80 mg capsules, once a day) and 1 healthy backup volunteer.
- ✓ Cohort 2 (C2) includes 10 healthy volunteers of the main group, each of whom will receive a single dose of PBTZ169 on an empty stomach at a dose of 960 mg (12 80 mg capsules, once a day) and 1 healthy backup volunteer.
- ✓ Cohort 3 (C3) includes 10 healthy volunteers of the main group, each of whom will receive PBTZ169 twice on an empty stomach at a dose of 640 mg (8 80 mg capsules, twice daily with a 12-hour interval; total daily dose 1280 mg) and 1 healthy backup volunteer.
- ✓ Cohort 4 (C4) includes 10 healthy volunteers of the main group, each of whom will receive a single dose of PBTZ169 on an empty stomach at a dose of 1280 mg (16 80 mg capsules, once a day) and 1 healthy backup volunteer.

Randomization will be done after hospitalization on the day before the first administration of the investigational product (Day 0 of the study) within each cohort by the envelope randomization method. Volunteers of each cohort (C1A, C1B, C2, C3 and C4) will be randomized at a ratio of 10:1:

- main therapy group 10 volunteers who will receive a single dose or two doses of the investigational product;
- group of backup volunteers 1 volunteer who receive one dose or two doses of the investigational product only if one of the volunteers of the main group of this cohort leaves the study before dosing and within 4 hours from the moment of dosing due to a reason unrelated to AE/SAE.

Volunteers of the main group and backup volunteers will be hospitalized in the evening on the day before the administration of the product, but at least 12 hours before planned administration of the product. Volunteers of the main group will be hospitalized for about 2.5 days, including the visit on the day of hospitalization, day of administration of the investigational product and 48 hours after the administration of the investigational product. Backup volunteers of cohorts of the *First stage* of the study will be discharged from

the hospital at least 4 hours after the administration of the last capsule by the last volunteer of the main group if there will be no need to replace a dropped out volunteer.

Administration of the product will start simultaneously in cohorts C1A and C1B. The use of the product in volunteers of the C2 cohort will begin after the administration of the product by volunteers of the C1A and C1B cohorts. In volunteers of the C3 and C4 cohorts, the product will be used at least 7 days after volunteers from the previous C2 cohort take the investigational product and after obtaining results of safety evaluation of the investigational product (adverse events, changes in vital signs, laboratory test results, ECG and physical examinations) in volunteers of the previous C2 cohort. In volunteers of the C3 and C4 cohorts, the investigational product will be used in case of dose-limiting toxicity (DLT) in less than 50% of volunteers from the C2 cohort.

All volunteers of the C1A and C1B cohorts will take the product on the same day in two periods (1 therapy day in each) between which there will be a carry-over period ( $\geq$ 6 days).

Order	Number of	Study	period
	volunteers	1	2
1	10	PBTZ169, 640	PBTZ169, 640
		mg (8 80 mg	mg (8 80 mg
		capsules), on an	capsules), after a
		empty stomach	standard meal
2	10	PBTZ169, 640	PBTZ169, 640
		mg (8 80 mg	mg (8 80 mg
		capsules), after a	capsules), on an
		standard meal	empty stomach

On an empty stomach the product is administered (by volunteers of cohorts C2 and C4, cohort C1A during period 1, cohort C1B during period 2) after 10 hours of night fasting, washing down 300 mL of bottled water. Each volunteer will administer 4 capsules within 2 minutes broken down into few portions, depending on the total number of capsules, washing down each portion with a few sips of water On the day of administration it is allowed to drink as much water as one wants except for 1 hour prior to administration of the product, during which water consumption is not allowed, and 4 hours after the administration of the product (during the first hour water consumption is not allowed, during the next 3 hours water consumption will be regulated: the volunteer will need to drink 100 mL of bottled water every hour). Within 4 hours after administration, volunteers will not be allowed to eat. 4 hours after administration, volunteers will receive a standard meal.

After food intake (by volunteers of the C1A cohort – during period 2, of the C1B cohort – during period 1) the medicinal product is administered 30 minutes (± 2 minutes) after the beginning of a standard breakfast, washing down with 300 mL of bottled water (within 2 minutes, 4 capsules broken down into few portions depending on the total number of capsules, washing down each portion with a few sips of water). Breakfast is provided after 10 hours of night fasting. On the day of administration it is allowed to drink as much water as one wants except for 30 minutes prior to administration of the product, during which water consumption is not allowed (except for that present in the breakfast), and 4 hours after the administration of the product (during the first hour water consumption is not allowed, during the next 3 hours water consumption will be regulated: the volunteer will need to drink 100 mL of bottled water every hour). Within 4 hours after administration, volunteers will not be allowed to eat. 4 hours after administration, volunteers will receive a standard meal.

Volunteers of the C3 cohort (two administrations) will take the product twice a day, washing down with 300 mL of bottled water each time (within 2 minutes, 4 capsules broken down into few portions depending on the total number of capsules, washing down each portion with a few sips of water). For the first time, volunteers of the C3 cohort will take the medicinal product in the morning on an empty stomach after 10 hours of night fasting, second time – 12 hours after the first administration after 3 hours of fasting. On the day of administration it is allowed to drink as much water as one wants except for 1 hour prior to each administration of the product, during which water consumption is not allowed, and 4 hours after each administration of the product (during the first hour water consumption is not allowed, during the next 3 hours water consumption will be regulated: the volunteer will need to drink 100 mL of bottled water every hour). Within 4 hours after each administration, volunteers will not be allowed to eat. 4 hours after the first administration, volunteers will receive a standard meal. Standard dinner will be offered to volunteers of the C3 cohort no later than 3 hours before the second administration of the medicinal product.

Each volunteer in the C1A, C1B, C2 and C4 cohorts will have their venous blood collected to determine the concentration of PBTZ169 and its metabolites before the administration of the product (point 0, blood sample in the range from -5 min to -1 min), and then at the following time points after the administration of the medicinal product: at 0:30, 1:00, 1:30, 2:00, 3:00, 4:00, 6:00, 9:00, 12:00, 24:00, 48:00 and 72:00 (h:min).

For volunteers of the C3 cohort (two administrations), venous blood will be collected to determine the concentration of PBTZ169 and its metabolites before the first administration of the medicinal product (point 0, blood sample in the range from -5 min to -1 min), and then within 72 hours at the following times points after each administration of the medicinal product: at 0:30, 1:00, 1:30, 2:00, 3:00, 4:00, 6:00, 9:00, 12:00 (the point before the second administration of the medicinal product in the range from -5 min to -1 min), 12:30, 13:00, 13:30, 14:00, 15:00, 16:00, 18:00, 21:00, 24:00, 48:00, 72:00 (h:min) after the first administration of the medicinal product.

During blood sampling for pharmacokinetics before the time point of 48:00 after the administration of the medicinal product, volunteers will be staying in the hospital and will be discharged after all procedures planned by the protocol have been completed, then follow-up will continue on an outpatient basis. After discharge from the hospital, volunteers will visit the research site in 1 day (on Day 4 volunteers of all cohorts and on Day 10 only volunteers of cohorts C1A and C1B). Venous blood samples will be collected from each volunteer at the time point of 72:00 after the administration of the medicinal product and follow-up procedures will be carried out. 5±1 days after the last administration of the medicinal product (on Day 12±1 of the study for volunteers of cohorts C1A and C1B or on Day 6±1 of the study for cohorts C2-C4), volunteers will visit the research site for to undergo procedures of follow-up visit (FUV; safety evaluation).

Point 0 before the administration of the medicinal product, including the point before the second administration of the medicinal product, can be within the range from -5 min to -1 min. For time points of 24:00, 48:00, 72:00 after the administration of the medicinal product, deviations of 10 minutes from the specified time are allowed in either direction ( $\pm 10$  min). For all other time points for blood sampling after the administration of the investigational medicinal product, deviations of not more than 2 min in either direction ( $\pm 2$  min) are allowed.

At each time point of blood sampling for the purpose of determination of the concentration of PBTZ169, additional venous blood samples will also be collected for storage for determination of additional parameters should it become necessary. A detailed description of the work with clinical blood samples for the purpose of study of pharmacokinetics will be provided in the instructions prepared by the central laboratory.

After the completion of the first part of the study, main samples (blood plasma samples of volunteers) will be sent to the central laboratory to determine the concentration of the investigational product PBTZ169 and its two metabolites (MET-11526124 3-OXO MET-11526115 3-OH). Additional samples (blood plasma samples of volunteers) will be stored in the research site in a freezer at a temperature not exceeding -65 °C until the end of the pharmacokinetic part of the study or until further directions from the Sponsor.

After the study is completed by the last volunteer from the *First stage* (C1A, C1B, C2, C3 and C4), safety and pharmacokinetics, as well as the effect of food will be analyzed based on the data of all cohorts who administered the product once or twice.

Based on the results of the evaluation of safety, pharmacokinetics and analysis of the effect of food after the end of the *First stage*, the Sponsor:

- ✓ will determine the dose for the study of PBTZ169 with repeated use in Phase 2 of the study.
- ✓ will decide on the mode of administration of PBTZ169: on an empty stomach or after meal, once a day or twice a day.
- ✓ can decide to adjust time points for sampling (if necessary, appropriate amendments will be made to the protocol);
- ✓ can decide to make changes to study procedures at Stage 2 (where necessary, appropriate amendments will be made to the protocol).

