### Evaluation of relative bioavailability and relative degree of absorption (to evaluate the effect of food with single dosing)

When evaluating the effect of food on the pharmacokinetics of PBTZ169, tested (T) method of administration will be 8 80 mg capsules after meal, reference (R) method - 8 80 mg capsules on an empty stomach. The study will evaluate relative bioavailability and relative degree of absorption.

Changes in PK parameters will be presented descriptively and graphically. After logarithmic conversion, primary PK parameters (Cmax and AUC) will be analyzed using ANOVA. Obtained point estimations and 90% confidence intervals for the difference between mean values of a PK parameter after its logarithmic transformation (lnT – lnR) are potentiated to obtain a point estimation and corresponding 90% confidence interval limits for the ratio of geometric means (T/R).

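### The food-effect crossover does not randomise volunteers to sequence: the only stated draw separates main volunteers from backups within a cohort

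*Combined protocol and SAP*

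**What the plan says.** All references are to the Combined protocol and SAP, section 1 Study Summary.

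- **Entry to a cohort.** Under the First stage heading: "Volunteers who meet the selection criteria for the study will be included in 5 cohorts". No mechanism for assigning a volunteer to one cohort rather than another follows.
- **Randomisation.** It takes place on Day 0, "within each cohort by the envelope randomization method". The ratio is given as "Volunteers of each cohort (C1A, C1B, C2, C3 and C4) will be randomized at a ratio of 10:1", and the two groups listed beneath it are the main therapy group (10) and the backup group (1). A backup is dosed "only if one of the volunteers of the main group of this cohort leaves the study" early for a reason unrelated to an adverse event.
- **Sequence.** The two-period table in the First stage text gives 10 volunteers for each order. The administration instructions show that C1A takes the product fasted and then fed, and C1B fed and then fasted. (The second cohort bullet is also labelled 1A; the later text makes clear that it is C1B.)
- **Timing.** "All volunteers of the C1A and C1B cohorts will take the product on the same day in two periods", and both cohorts start together.
- **Sites.** "It is planned to involve up to 2 research sites in the Russian Federation".
- **Use of the result.** The food effect is a main objective. Log-transformed Cmax and AUC go into an ANOVA that yields a fed/fasted ratio with a 90% confidence interval. The Statistical methods text does not mention allocation to sequence.

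**The concern.** In a two-sequence, two-period crossover, the allocation that supports the comparison is the allocation to sequence. Here the cohort is the sequence, and the draw is made inside the cohort, so it comes too late to allocate sequence. The plan randomises who stands by as a backup but not who takes which order. It does not say that site or enrolment order decides the matter, but filling C1A at one site and C1B at the other would comply with the text as written.

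The fed/fasted ratio has the only confidence interval planned in the study. It is also one of the inputs from which the sponsor chooses fasted or fed administration for the 14-day second stage. If the two groups differ in how their exposure changes from period 1 to period 2, that difference enters the food-effect estimate.

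**Working it through.** **Plan's own figure.** Planned enrolment is up to 69. Six cohorts of 10 main volunteers, plus 5 first-stage backups, plus 4 possible backups in C5: 60 + 5 + 4 = 69. The figure reproduces. C1A and C1B account for 2 × 11 = 22 of these, 20 of them main volunteers. No power calculation, within-subject CV or margin is given for the food effect, so there is no other figure to reproduce.

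**What cancels and what does not.** Let τ be the true log fed/fasted ratio, and p1 and p2 the period effects (period 2 minus period 1, log scale) in C1A and C1B.

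- C1A (fasted, then fed): E[lnT − lnR] = τ + p1
- C1B (fed, then fasted): E[lnT − lnR] = τ − p2
- Average of the two: τ + (p1 − p2)/2

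Overall exposure levels do not appear, because each volunteer is their own control. If p1 = p2, the period effect disappears. The bias is (p1 − p2)/2. With two sequences and two periods, this quantity and τ cannot both be estimated, so no choice of ANOVA terms removes it.

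**Size of the bias.** The drifts are assumptions; the documents give none. For a differential drift d, the bias factor on T/R is exp(ln(1 + d)/2).

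| Differential drift | ln(1 + d)/2 | Factor on T/R |
|---|---|---|
| 0% | 0.0000 | 1.000 |
| 5% | 0.0244 | 1.025 |
| 10% | 0.0477 | 1.049 |
| 20% | 0.0912 | 1.095 |

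**Coverage of the nominal 90% interval.** N = 20, 18 degrees of freedom, t(0.95) = 1.734, SE = √ln(1 + CV²) × √(2/20). The CVs are assumptions. Coverage is the probability that a non-central t with non-centrality bias/SE lies within ±1.734. For example, at CV 30% and 10% drift the non-centrality is 0.0477/0.0928 = 0.51.

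| CV | SE | 0% | 5% | 10% | 20% |
|---|---|---|---|---|---|
| 20% | 0.0626 | 0.900 | 0.876 | 0.810 | 0.595 |
| 30% | 0.0928 | 0.900 | 0.889 | 0.859 | 0.753 |
| 40% | 0.1218 | 0.900 | 0.894 | 0.876 | 0.813 |

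A simulation at CV 30% (40,000 runs) gave 0.902, 0.859 and 0.752 at 0%, 10% and 20% drift.

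**Check of the algebra.** In a second simulation (20,000 runs, true T/R 1.50, within-subject SD 0.294), a pure level difference of 0.3 log units between cohorts left the estimate at 1.499. A cohort-by-period difference of 0.1 or 0.2 log units moved it to 1.576 or 1.658, as the formula predicts: 1.50 × exp(0.05) = 1.577 and 1.50 × exp(0.10) = 1.658.

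**With both sequences at each site.** If each site has 5 main volunteers per sequence, a site-specific drift enters once with a plus and once with a minus sign and cancels. In simulation the mean T/R relative to truth was 1.000 at 10% site drift and 1.001 at 20%, the latter within simulation noise.

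**The case against.** The strongest reply has four parts.

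- **The text reviewed is a study summary.** A fuller section on randomisation might allocate sequence. This limits the claim to what the summary states. But the summary does describe a randomisation, says at which level it is done and names the groups it forms; sequence is not among them.
- **The harm needs several conditions.** The clearest route to bias requires two sites, a food-effect part split between them, a split along sequence, and a drift that differs by site over a gap of at least 6 days. None of these is stated to be planned, and meals, fasting, water and sampling times are tightly standardised. This stands as a limit on likelihood: no bias has been demonstrated.
- **The assumed bias is small next to the imprecision.** At CV 30% the interval already runs from 0.851 to 1.175 times the estimate (exp(±1.734 × 0.0928)), and 10% drift shifts the ratio by only 4.9%. The summary sets no margin or pass/fail rule, so no decision can be shown to change. This also stands, and it keeps the point from being critical. But imprecision is reported by the interval; this bias would not be.
- **Stratifying by site is awkward with 11 volunteers per sequence.** Equal numbers of each sequence at each site are still possible, for example 6 + 6 at one site and 5 + 5 at the other (12 + 10 = 22). The real difficulty is that there is only one backup per sequence, who can be at only one site.

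**Conclusion.** The concern holds. Followed as written, the study summary never randomises the fasted/fed order on which its only planned confidence interval rests. The estimate is not invalid: level differences, a common period effect and calendar time are already dealt with. What is left is a differential period change, with a bias of half its size on the log scale: 0% to 9.5% in T/R for assumed drifts of 0% to 20%, with 90% interval coverage between 90% and 75% at an assumed CV of 30%. The actual drift and CV are unknown, and the drift may be zero. The change should be made because such a bias could be neither separated nor corrected afterwards, while preventing it costs very little.

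**What to change.** In the First stage text, replace the within-cohort draw for the food-effect part with a single randomisation: on Day 0 the 22 volunteers are allocated 1:1 to C1A or C1B, 10 main and 1 backup in each, with backup status on the same list. The 10:1 draw can stay as it is for C2, C3 and C4. If two sites take part, either run the food-effect part at one site or stratify the list by site so that both sequences occur in equal numbers at each. If randomisation to sequence is already intended, state the rule here.

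The cost is a new list and new envelopes, because envelopes prepared for a 10:1 draw within a cohort cannot allocate sequence. All 22 volunteers already share the same Day 0 and the same dosing days, so total enrolment (up to 69), timing and precision do not change. If the part is split over two sites, a backup for a given sequence may not be at the site where one is needed; running it at one site avoids this.

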### Justification of dose choice

#### Dose selection for single administration

To date, two clinical studies of PBTZ169 have been completed: Phase I clinical study (protocol No. PBTZ169-Z00-C01-1), where PBTZ169 was first used in humans, and Phase IIa clinical study (protocol No. PBTZ169-A15-C2A-1), where the medicinal product PBTZ169 was used in patients with newly diagnosed respiratory

tuberculosis with bacterial excretion and preserved sensitivity to isoniazid and rifampicin.

Based on the results of analysis of pharmacokinetics of PBTZ169 in these studies, it was decided to further study the product in higher doses in healthy volunteers. The highest dose in the two previous clinical studies of PBTZ169 was 640 mg. The 640 mg dose was well tolerated both by volunteers of the Phase I study and by patients of the Phase IIa study, at a dose of 640 mg the medicinal product had an acceptable safety profile. During the Phase I study, the only case of dose-limiting toxicity (DLT) recorded during the study was related to an increase in blood glucose after a single dose of 80 mg. During the Phase I study, no serious adverse event was recorded. 6 AEs had a relationship with the investigational product, the following AEs were recorded during the study: headache (4 cases in 4 volunteers, *possible relationship*), leukocytosis (1 case in 1 volunteer, *possible relationship*).

In the Phase IIa study, there was one serious adverse event of moderate severity, without a connection with the medicinal product – a spontaneous tuberculous-related paraproctitis in one patient (from the group receiving the medicinal product at a dose of 640 mg), which led to withdrawal of the medicinal product and subsequent drop-out of the patient. Possible relationship with therapy with the investigational product was suspected in 4 cases of AEs, all of which were in a patient who dropped out of the study due to SAE. In both studies, as the dose increased, no increase in the frequency of AEs was observed.

To study the effect of food, in this study it was decided to use the maximum dose that had been studied in the previous two clinical studies (640 mg), which had an acceptable safety profile.

Calculation of doses for single use is done based on recommendations provided in Guidelines for Determination of a Safe Dose of Medicinal Product for Phase I Clinical Studies in Adult Volunteers (Guidelines for Pre-Clinical Studies of Medicinal Products, Part One, 2012).

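### The rule for starting C2 (960 mg) does not say which C1 period it follows and asks for no C1 safety results; a minor gap that is cheap to close

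*Combined protocol and SAP*

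**What the plan says.** All of this is in section 1 (Study Summary), mainly under the First stage heading.

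- **Start of C2.** Dosing "will begin after the administration of the product by volunteers of the C1A and C1B cohorts". No other condition is attached.
- **C1 has two dosing days.** Each C1 volunteer is one "each of whom will receive PBTZ169 only twice", once fasted and once fed. The timing is given as "All volunteers of the C1A and C1B cohorts will take the product on the same day in two periods", with at least 6 days between them.
- **Start of C3 and C4.** These cohorts are dosed "at least 7 days after volunteers from the previous C2 cohort take the investigational product". A second condition is that dosing comes only "after obtaining results of safety evaluation of the investigational product" in C2, and a third is that fewer than half of the C2 volunteers had a dose-limiting toxicity (DLT).
- **Observation after each C1 dose.** Volunteers stay in hospital for 48 hours and return a day later: "on Day 4 volunteers of all cohorts and on Day 10 only volunteers of cohorts C1A and C1B". At that visit blood is taken "at the time point of 72:00 after the administration of the medicinal product and follow-up procedures will be carried out". The summary does not list what those procedures are.
- **Earlier experience.** Under the dose selection heading: "The highest dose in the two previous clinical studies of PBTZ169 was 640 mg". The same text reports that this dose was well tolerated in both studies and that adverse events did not become more frequent as the dose rose.

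**The concern.** C2 is the first cohort to go above the earlier 640 mg maximum, yet it has the loosest entry rule of the escalation steps. Because C1 is dosed twice, the phrase about C1 having taken the product has two readings, and up to two sites may have to apply it.

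If period 1 is enough, the rule taken literally lets C2 be dosed while C1 volunteers are still in hospital and before their Day 4 visit, so that laboratory, ECG and adverse event results from C1 need not have been seen. C1A and C1B put 20 volunteers on 640 mg in period 1, ten of them fasted as in C2. These are the trial's own data at the dose just below 960 mg, and the rule does not require anyone to look at them first.

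**Working it through.** The plan gives no power, alpha or sample-size figure on this point, so there is none to reproduce. The check sets the two entry rules side by side and works out the calendar.

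| | C1 to C2 | C2 to C3 and C4 |
|---|---|---|
| Period named | No (C1 has two) | Not needed (C2 has one dosing day) |
| Minimum wait | None stated | 7 days = 7 × 24 = 168 hours |
| Safety results required | No | Yes |
| DLT limit | None stated | Fewer than 50% of C2 |

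**Could another rule in the summary fill the gap?** The formal analysis comes after the last First stage volunteer finishes. The section on choosing the repeated dose applies the DLT criterion to that choice. The monitoring board appears only in a footnote on the Cohort 5 dose. None of these governs the start of C2.

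**Dose step.**
- Ratio: 960/640 = 1.5. Increment: 960 − 640 = 320 mg.
- Phase I steps (40, 80, 160, 320, 640 mg) were increments of 40, 80, 160 and 320 mg, each a doubling. The C2 increment equals the largest of these and is smaller in relative terms.
- Against the human dose equivalent to the rat no-effect level (2100 mg for 70 kg): 960/2100 = 0.457, about 46%.
- The gated step from C2 to C4 is 1280/960 = 1.33, also 320 mg.

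**Calendar, with the first C1 dose on Day 1.**
- Period 1 72-hour visit: 1 + 3 = Day 4, as stated.
- Period 2 dosing: 10 − 3 = Day 7 from its 72-hour visit, and 12 − 5 = Day 7 from the follow-up visit. The two agree.
- Earliest C2, *assuming next-morning dosing*: Day 2 if period 1 suffices, which is 24 hours after the first C1 dose and 24/48 = half of the inpatient stay. Day 7 + 1 = Day 8 if both periods are meant.

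**Effect of requiring review of period 1 results.**
- *Assuming 1 to 2 days after the Day 4 visit* for results and review, the condition is met on Day 5 or 6, that is, 4 to 5 days after the first C1 dose. This is lighter than the 7-day wait before C3 and C4.
- Delay on the period 1 reading: 5 − 2 = 3 days, or 6 − 2 = 4 days.
- Delay on the both-periods reading: none, since Day 5 or 6 comes before Day 8.
- Share of a 7-month study: 7 × 365.25/12 = 213 days, so 3/213 = 1.4% to 4/213 = 1.9%.

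**The case against.** The strongest reply is that the two steps are not alike. C1 repeats a dose already used in two completed studies, and it was chosen for the food-effect question because it had an acceptable safety profile. The support for 960 mg therefore existed before this trial. C2 is the first new dose, and the plan places its full gate directly after it. This stands, and it is why the risk is small and why no 7-day wait or DLT limit is proposed for C2. The documents do not, however, give it as the reason for having no C1 gate, and it does not settle which period is meant.

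Second, since C1 volunteers take the product twice, the sentence can fairly be read as after both doses. That also stands. A replacement condition tied to period 1 alone could let C2 start on Day 5 or 6 instead of Day 8 and so loosen the plan. The fix must add to the sentence and not replace it.

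Third, the Day 2 start needs both the looser reading and next-morning dosing, and no schedule states either. Day 2 is what the wording permits, not what is planned.

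Fourth, a review with no stopping criterion may change no decision, and half of the period 1 volunteers are fed while C2 is fasted. It is true that no effect on a C2 decision has been shown. The review only ensures that results already being collected are seen before the dose goes up. The ten fasted volunteers are the direct comparison, and the fed ten add tolerability data at the same dose.

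Finally, the text reviewed is the summary in section 1. If a fuller section already sets a rule between C1 and C2, the summary only needs to match it.

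**Conclusion.** The point holds as a minor safety improvement. The start rule for C2 has two readings, about six days apart (Day 2 or Day 8, assuming next-morning dosing), and under neither does it require C1 safety results, although the plan asks for the previous cohort's results at the next step.

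A reader might infer more, and the documents do not support it:

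- *That the step to 960 mg is too large.* It equals the largest Phase I increment, is smaller in relative terms than the Phase I doublings, and stays at about 46% of the no-effect equivalent dose.
- *That earlier data signal danger above 640 mg.* The only Phase I DLT, a rise in blood glucose, came after 80 mg, and adverse events did not increase with dose. That case shows that a relevant event can be a laboratory finding. It does not show a dose-related risk.
- *That C1 data would go unseen until the end of the First stage.* The summary describes a formal analysis at that point. It does not say that the investigator or sponsor would not look earlier.

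The conclusion rests on the summary text alone. The calendar figures also rest on next-morning dosing and on 1 to 2 days for results and review, both of which are assumptions.

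**What to change.** Keep the existing sentence on the start of C2, state whether it refers to period 1 or to both C1 periods, and add:

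> and in any case not before all C1A and C1B volunteers have completed period 1 observation through the Day 4 visit and the period 1 safety results already scheduled (adverse events, vital signs, laboratory tests, ECG, physical examination) have been obtained and reviewed by the investigator and sponsor.

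Because this is a minimum, a start after both periods is preserved if that was the intention. No new procedure, DLT limit or pharmacokinetic requirement is needed. The summary does not show which tests fall by Day 4, so the review should cover only what the schedule of assessments already plans for period 1.

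The cost is one clarification and one added clause. There is no delay if both periods were meant. If only period 1 was meant, C2 starts about 3 to 4 days later, or 1.4% to 1.9% of the planned 7 months, on the assumptions above.
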